### 14.5. Primary Analysis (For Part 1)

#### **Lid Margin Staining (LMS)**

**Model-1:** Upper and lower eyelids' average LMS (average of Horizontal and sagittal grades) after 14-hours follow-up will be analyzed using a linear mixed model by adjusting the baseline LMS as a covariate.

**Model-2:** Final eyelid's average (average of the upper and lower lid average) LMS after 14-hours follow-up will be analyzed using a linear model by adjusting the baseline LMS as a covariate.

Both the models will include subject strata (asymptomatic/symptomatic) as fixed effect, however, only model-1 will include subject as random effect (G-side). Other characteristics such as age, gender, and race will be included as fixed covariates when appropriate. For only model-1, different covariance structures will be considered to model the residual errors between the lower and upper eyelids' average LMS from the same subject (R-side). The covariance structure will be selected based on the finite-sample corrected Akaike's Information Criterion. The following covariate structures will be considered:

- Unstructured Covariance Structure (UN)
- Homogenous Compound symmetry (CS)

# Clinical Study Protocol

## Johnson & Johnson Vision Care, Inc.

Comparisons between subject strata for LMS will be carried out using a one-sided 95% CI of least-square means differences (symptomatic - asymptomatic) at 14-hour follow-up for the hypothesis given below:

$$H_0: \mu_S - \mu_A \leq 0$$
$$H_A: \mu_S - \mu_A > 0,$$

where S=Symptomatic and A=Asymptomatic. For only model-1, adjustments for multiple comparisons across lower and upper eyelids' will be performed using a simulation method with alpha equal to 0.05 (Edwards and Berry, 1987). A statistically greater upper and lower LMS, on average, for symptomatic subjects compared to asymptomatic subjects after 14 hours of lens wear will be concluded if the lower limit of the 95% confidence intervals for the least-squares means is greater than 0.

### **Non-invasive tear break-up time (NIBUT) and Tear Meniscus Height (TMH)**

NIBUT and TMH will be analyzed using a linear mixed model separately by adjusting the baseline as a covariate. The model will include subject strata (asymptomatic/symptomatic), time event (i.e., fitting and 14-hours follow-up), and strata by time event interaction as fixed effects; subject will be included as random effects (G-side). Other characteristics such as age, gender, and race will be included as fixed covariates when appropriate. Different covariance structures will be considered to model the residual errors between the repeated measurements within time event from the same subject (R-side). The covariance structure will be selected based on the finite-sample corrected Akaike's Information Criterion. The following covariate structures will be considered:

- Unstructured Covariance Structure (UN)
- Homogenous Compound symmetry (CS)
- Heterogeneous Compound Symmetry (CSH)
- Spatial Power (SP[POW])

For SP(POW) covariance structure, subject and time event within subject will be included as random effects. For the remaining structures, only subject will be included as a random effect. The structure that returns the lowest Akaike Information Criteria Corrected (AICC) will be selected as the structure that best fit the data. Heterogeneous covariance structures across strata may be considered if necessary. The Kenward and Roger method (Kenward and Roger, 1997) will be used for the denominator degree of freedom.

Comparisons between subject strata for NIBUT and TMH will be carried out using a one-sided 95% CI of least-square means differences (symptomatic - asymptomatic) at 14-hour follow-up for the hypothesis given below:

$$H_0: \mu_S - \mu_A \geq 0$$
$$H_A: \mu_S - \mu_A < 0.$$

where S=Symptomatic and A=Asymptomatic. No multiple adjustment will be necessary since the hypothesis test will be conducted based on only 14-hour follow-up. A statistically shorter

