### **Tear Film Osmolarity (TOSM)**

TOSM will be analyzed using a linear mixed model by adjusting the baseline TOSM as a covariate. The model will include subject strata (asymptomatic/symptomatic), time event (i.e., fitting and 14-hours follow-up), and strata by time event interaction as fixed effects; subject will be included as random effects (G-side). Other characteristics such as age, gender, and race will be included as fixed covariates when appropriate. Different covariance structures will be considered to model the residual errors between the repeated measurements within time event from the same subject (R-side). The covariance structure will be selected based on the finite-sample corrected Akaike's Information Criterion. The following covariate structures will be considered:

- Unstructured Covariance Structure (UN)
- Homogenous Compound symmetry (CS)

The structure that returns the lowest Akaike Information Criteria Corrected (AICC) will be selected as the structure that best fit the data. Heterogeneous covariance structures across strata may be considered if necessary. The Kenward and Roger method (Kenward and Roger, 1997) will be used for the denominator degree of freedom.

Comparisons between subject groups for TOSM will be carried out using a one-sided 95% CI of least-square means differences (symptomatic - asymptomatic) at 14-hour follow-up for the hypothesis given below:

$$\begin{aligned} H_0: \mu_S - \mu_A &\leq 0 \\ H_A: \mu_S - \mu_A &> 0, \end{aligned}$$

where S=Symptomatic and A=Asymptomatic. No multiple adjustment will be necessary since the hypothesis test will be conducted based on only 14-hour follow-up. A statistically greater TOSM, on average, for symptomatic subjects compared to asymptomatic subjects after 14 hours of lens wear will be concluded if the lower limit of the 95% confidence intervals for the Least-squares means is greater than 0.

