### **14.7. Other Hypotheses**

#### **For Part 2:**

The analysis procedure will follow the exact steps for analyzing these hypotheses as described in the primary analysis section for LMS, NIBUT, TMH, TOSM, and WBC.

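### The primary NIBUT, TMH and osmolarity models use one baseline slope for both readings, so the 14-hour stratum contrast is biased if that slope changes during the day and the strata also differ at baseline

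*Combined protocol and SAP*

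**What the plan says.** Protocol section 14.5 specifies the NIBUT and TMH models as follows: "NIBUT and TMH will be analyzed using a linear mixed model separately by adjusting the baseline as a covariate". The fixed effects are then listed: "The model will include subject strata (asymptomatic/symptomatic), time event (i.e., fitting and 14-hours follow-up), and strata by time event interaction as fixed effects". The only further covariates are these: "Other characteristics such as age, gender, and race will be included as fixed covariates when appropriate". No baseline-by-time-event term appears.

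Osmolarity has the same structure: "TOSM will be analyzed using a linear mixed model by adjusting the baseline TOSM as a covariate", with the same stratum, time-event and interaction terms. The test uses one time point: "No multiple adjustment will be necessary since the hypothesis test will be conducted based on only 14-hour follow-up".

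Section 14.7 carries the models into Part 2: "The analysis procedure will follow the exact steps for analyzing these hypotheses as described in the primary analysis section".

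Lid margin staining is handled differently. In Model-2 the final eyelid average "after 14-hours follow-up will be analyzed using a linear model by adjusting the baseline LMS as a covariate", and Model-1 likewise uses only 14-hour values, so the staining slope belongs to 14 hours.

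**The concern.** The fitting reading is taken at the same morning visit as the pre-lens baseline. The other reading comes about 14 hours later. There is no particular reason for baseline to predict both equally well, yet the listed model gives it a single coefficient. The fitting reading, which is not tested, therefore helps to set the adjustment applied to the 14-hour contrast.

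In a randomised comparison the expected baseline difference would be zero and this would cost only precision. Here the strata are CLDEQ-8 groups in a non-randomised study (sections 4.1 and 5.1), and the introduction expects these measures to differ between them. A baseline difference is therefore plausible, and a wrong slope multiplied by a real difference is a bias. Three of the five primary measures, and their Part 2 repeats, are exposed to it.

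**Working it through.** **The plan's own figure.** Table 11 gives 81% power for NIBUT at a difference of -2.1 s, SD 3, 27 per stratum. The standard error is 3 × √(2/27) = 0.816 and the ratio is 2.1/0.816 = 2.57. A one-sided 5% t-test on 52 df gives 81.4%, so the figure reproduces (two-sided would give 71.4%). One-sided 5% is used below, as in section 14.5.

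**Bias formula.** Because stratum by time is saturated and the data are balanced, the fitted 14-hour contrast is

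D14 - b_pooled × Dbase,

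where D14 and Dbase are the symptomatic-minus-asymptomatic differences at 14 hours and at baseline. The correctly adjusted contrast uses b_14. Hence

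bias = (b_14 - b_pooled) × Dbase.

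Under compound symmetry b_pooled = (b_fit + b_14)/2. Under an unstructured covariance it leans toward the less noisy reading. With assumed residual variances of 0.36 (fitting) and 0.96 (14 hours), uncorrelated given baseline, the fitting slope gets weight 0.96/(0.36 + 0.96) = 0.73. With slopes 0.8 and 0.2 and Dbase = -0.5 SD, the bias is then 0.22 SD, against 0.15 SD under compound symmetry.

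**Inputs from Tables 6 to 8.** SDs are pooled over strata.

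- NIBUT: SD 8.24 at fitting, 4.63 at 14 hours; fitting difference 11.47 - 13.19 = -1.72 s.
- Osmolarity: SD 59.6 and 45.5; fitting difference 297.47 - 319.52 = -22.05 mOsm/L.
- Lower-lid TMH: baseline 0.21 in both strata, so Dbase = 0.00.

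**Assumed, because not given:** the correlations of each reading with baseline; a baseline SD equal to the fitting SD; and, for NIBUT and osmolarity, a baseline difference equal to the fitting difference.

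**Are the slopes likely to differ?** A slope is correlation × SD(Y)/SD(baseline). For NIBUT, equal slopes need the 14-hour correlation to be 8.24/4.63 = 1.8 times the fitting correlation, which is unlikely. For TMH the lower-lid SD rises from about 0.054 to 0.066, so a correlation falling from 0.70 to 0.70 × 0.0542/0.0655 = 0.58 gives equal slopes.

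**Osmolarity**, compound symmetry, true adjusted difference zero. Error rates are from simulation, 20,000 trials per row.

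| Correlation, fitting/14 h | b_fit | b_14 | b_pooled | Bias (mOsm/L) | One-sided error |
|---|---|---|---|---|---|
| 0.5/0.5 | 0.50 | 0.38 | 0.44 | +1.3 | 4-6% |
| 0.6/0.4 | 0.60 | 0.31 | 0.45 | +3.2 | 7-8% |
| 0.7/0.3 | 0.70 | 0.23 | 0.46 | +5.2 | 10-11% |
| 0.8/0.2 | 0.80 | 0.15 | 0.48 | +7.1 | 13% |

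The 13% uses the true standard error of the estimate. The compound-symmetry standard error gives about 16%, but that also absorbs unequal residual variances, a separate matter. With a 14-hour slope the error is about 5% in every row.

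**NIBUT in the Table 11 cell.** Everything is scaled by 3/4.63, so that the 14-hour SD is 3: baseline and fitting SD 8.25 × 3/4.63 = 5.35, Dbase = -1.72 × 3/4.63 = -1.11 s. At 0.7/0.3:

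- b_fit = 0.70; b_14 = 0.3 × 3/5.35 = 0.168; b_pooled = 0.434.
- Bias = (0.168 - 0.434) × (-1.11) = +0.30 s, so -2.1 s is estimated as about -1.8 s.
- SE as written ≈ √[(2/27)(9 + 0.434² × 28.6 - 2 × 0.434 × 0.3 × 3 × 5.35)] = √[(2/27)(10.2)] = 0.87.
- SE with the 14-hour slope ≈ √[(2/27) × 9 × (1 - 0.09)] = 0.78.

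Simulation, which also carries the uncertainty in the slope, gives SEs of 0.88 and 0.79. Power is about 65% as written (with its true SE) and 83 to 84% with the 14-hour slope.

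**Same case with Dbase = 0.** There is no bias, but the SE is still 0.87 against 0.79, and power about 77% against 83 to 84%.

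**TMH.** With Dbase = 0.00, expected bias is zero.

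**The case against.** Several points on the other side stand.

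- A reader might infer that a fading baseline slope, common to both strata, is enough by itself to create a stratum difference. It is not: with equal expected baselines the expected bias is zero. The one pre-lens baseline pair documented for these measures on the lid that is measured, lower-lid TMH, is equal.
- A reader might infer an expected false positive for osmolarity. The plan's hypothesis is higher osmolarity in symptomatic subjects. If baselines follow it and slopes fade, the error works against the claim, as it does for NIBUT and TMH. The opposite direction rests on the historical fitting means, which are post-insertion and imprecise: -22.05 with SE √(75.538²/25 + 10.899²/16) = 15.4 (95% interval about -54 to +10). The NIBUT stand-in, -1.72 s, has SE 2.50 (interval -6.8 to +3.4).
- A reader might combine the 14-hour SD of 3 from Table 11 with the fitting SD of about 8.2 from Table 6 and conclude that NIBUT power drops below one half. That SD ratio, about 2.75, is in no table; Table 6 itself gives 1.8.
- The simple average of slopes holds only under compound symmetry, and the plan selects its covariance structure by AICC. The simulations used subject means rather than replicate readings, and Satterthwaite degrees of freedom rather than Kenward-Roger.
- Section 14.1 calls the text a general description and defers detail to a stand-alone SAP, which may contain the term.

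These points limit what can be said about size and sign. They do not change the model as written, and the documents give no reason for borrowing a slope from a time point that is not tested.

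**Conclusion.** The concern holds in conditional form. As listed, the NIBUT, TMH and osmolarity models impose one baseline slope on two readings and test only the second. The 14-hour contrast is biased when two conditions hold together: the slope changes between fitting and 14 hours, and the strata differ at baseline. Selection on symptoms makes the second plausible. If only the first holds, the cost is precision.

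Neither size nor direction can be settled from the documents, which give no correlations with baseline and no pre-lens NIBUT or osmolarity means. The osmolarity error of about 7 to 13% and the NIBUT power of about 65% against 83% are illustrations under assumed correlations and stand-in baseline gaps. Equal slopes would give no bias. For TMH none is expected if the historical baseline equality repeats.

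This is a specification weakness worth correcting because the correction is cheap. It does not show that any of the three primary tests will mislead.

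**What to change.** In section 14.5, in both the NIBUT/TMH and the osmolarity paragraphs, add a baseline-by-time-event interaction to the fixed effects, and state that the 14-hour least-squares means are taken at the overall baseline mean. Section 14.7 then carries the change into Part 2. Alternatively, model the 14-hour readings alone on baseline and stratum, as is already done for lid margin staining.

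The cost is one degree of freedom per model and a sentence of wording in the protocol or stand-alone SAP before database lock. No new data are needed. If the slopes are in fact similar, the 14-hour standard error may rise by up to about 4%; in most simulated settings it was unchanged or smaller.

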# Clinical Study Protocol

## Johnson & Johnson Vision Care, Inc.

- Unstructured Covariance Structure (UN)
- Homogenous Compound symmetry (CS)

The structure that returns the lowest Akaike Information Criteria Corrected (AICC) will be selected as the structure that best fit the data. Heterogeneous covariance structures across strata may be considered if necessary. The Kenward and Roger method (Kenward and Roger, 1997) will be used for the denominator degree of freedom.

The Comparison between the symptomatic and the asymptomatic strata will be carried out using one-sided 95% confidence intervals for the Least-squares means risk ratio (symptomatic over asymptomatic) at 6-hour follow up for the hypothesis given below:

$$\begin{aligned} H_0: \mu_S / \mu_A &\leq 1 \\ H_A: \mu_S / \mu_A &> 1, \end{aligned}$$

where S=Symptomatic and A=Asymptomatic. Adjustments for multiple comparisons across lower and upper lid margins will be performed using a simulation method with alpha equal to 0.05 (Edwards and Berry, 1987). A statistically significantly greater density of WBC, on average, in both the upper and lower lid margins for symptomatic subjects compared to asymptomatic subjects after 6 hours of lens wear will be concluded if the multiple adjusted lower limit of the 95% confidence intervals for the Least-squares means risk ratio is above 1.0.

**Remark:** For all the above models, the Kenward and Roger method implemented with the *kr2* option in SAS will be used for the calculation of the denominator degrees of freedom. Heterogenous models across subject strata may be considered. The log-likelihood ratio test will be used to test for homogeneity between the two strata. Convergence limitations will be taken into account as necessary. If convergence is problematic, then reduced versions of the corresponding model will be considered. When the normality assumption does not hold for an endpoint, the analysis will be conducted on transformed data; generalized linear models or generalized linear mixed models with appropriate distributions will also be considered on the original data.

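### The primary NIBUT, TMH and osmolarity models give the fitting and 14-hour readings common variance parameters; at the historical SDs this would make the 14-hour NIBUT interval about 1.4 times too wide

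*Combined protocol and SAP*

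**What the plan says.** Section 14.5 specifies one model form for NIBUT and TMH and a near-identical one for osmolarity. All three adjust for baseline and include stratum, "time event (i.e., fitting and 14-hours follow-up), and strata by time event interaction as fixed effects". Both time events are therefore in the response.

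- **Residual side.** The candidate structures are there to "model the residual errors between the repeated measurements within time event from the same subject (R-side"). They describe the two or three replicates taken at one time event. The candidates are UN, CS, CSH and SP(POW) for NIBUT and TMH, and UN and CS for osmolarity.
- **Random effects (NIBUT and TMH).** Under SP(POW), "subject and time event within subject will be included as random effects". Otherwise: "For the remaining structures, only subject will be included as a random effect". The osmolarity model has a subject effect only.
- **Heterogeneity.** "Heterogeneous covariance structures across strata may be considered if necessary". The Remark that closes 14.5 adds: "The log-likelihood ratio test will be used to test for homogeneity between the two strata".
- **Non-normality.** The same Remark says: "When the normality assumption does not hold for an endpoint, the analysis will be conducted on transformed data", with generalized linear models also to be considered.
- **Decision rule (NIBUT and TMH; the osmolarity rule uses the same interval).** "one-sided 95% CI of least-square means differences (symptomatic - asymptomatic) at 14-hour follow-up". The fitting readings play no part in the hypothesis.

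Section 14.7 carries the same analysis into Part 2.

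**The concern.** UN and CSH can let the first replicate vary more than the second, but the same block then applies at fitting and at 14 hours. The subject effect has one variance for both events. The time-within-subject effect under SP(POW) also has one variance. Nothing lets the spread of subject means differ between the two events.

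The stratum-by-time interaction protects the 14-hour point estimate. It does not protect its standard error, which comes from the common variance. If readings are more variable at fitting than at 14 hours, the 14-hour interval is too wide and power is lost. If they are less variable, the interval is too narrow and the test is too liberal. The protocol's own historical tables give SDs at both events, so the assumption can be checked.

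**Working it through.** **1. The plan's own figure.** Table 11 gives 81% for a difference of -2.1 and SD 3 with 27 per stratum. A two-sample t-test at one-sided 5% (noncentral t, 52 df) gives 81.4%; two-sided 5% gives 71.4%. All cells of Tables 11 to 13 reproduce one-sided. These tables use a single 14-hour SD, so they describe a test on 14-hour data and not the stacked model. One-sided 5% is used below, as in 14.5.

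**2. Formula.** With equal strata, a stratum-by-time interaction and common variance parameters, the variance behind the 14-hour contrast is the mean of the two event variances:

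- SE factor k = sqrt( ((V_fit + V_14)/2) / V_14 )
- actual one-sided size = 1 - Φ(1.645 × k)

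**3. NIBUT.** Table 6 SDs (asymptomatic, symptomatic) are 8.917 and 7.035 after insertion, and 4.608 and 4.660 at 14 hours. The post-insertion row is taken as the fitting event.

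| Weighting | V_fit | V_14 | Ratio | k | Size |
|---|---|---|---|---|---|
| Equal strata (as planned) | 64.50 | 21.47 | 3.00 | 1.41 | 1.0% |
| Historical df 24/15 | 67.97 | 21.42 | 3.17 | 1.44 | 0.9% |

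Both strata agree in direction (variance ratios 3.74 and 2.28). Treated as an F ratio on 39 and 39 df, ignoring pairing, 3.17 has a 95% interval of about 1.7 to 6.0.

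Power at the historical difference, 8.34 - 9.46 = -1.12 s, with equal strata:

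- correct SE = sqrt(21.47 × 2/27) = 1.26; power = Φ(1.12/1.26 - 1.645) = 22%
- common-variance test: Φ(1.12/1.26 - 1.645 × 1.415) = 7.5%, or about 8%

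Simulation with 27 per stratum, a baseline covariate and assumed correlations (0 to 0.6 between events, 0 to 0.5 with baseline) gave k of 1.39 to 1.43, size of about 0.9 to 1.1%, and power of 8 to 10% against 22 to 26%. With a separate 14-hour variance the size returned to 4.3 to 5.5%.

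**4. How far the NIBUT factor could shrink.**

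- *Baseline adjustment.* Table 6 gives no baseline row, so its strength must be assumed. If baseline explains 50% of the fitting variance and 20% of the 14-hour variance, k is 1.20 to 1.22 and size 2.2 to 2.4%.
- *Log scale.* Taking log variance = ln(1 + (SD/mean)²) from Table 6, the ratio falls to 1.44 to 1.50, k to 1.10 to 1.12, and size is 3.3 to 3.5%.

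**5. Lower-lid TMH (the lid measured here).** Table 7 SDs are 0.056 and 0.048 after insertion, and 0.065 and 0.067 at 14 hours. With equal strata V_fit = 0.00272 and V_14 = 0.00436, so k = 0.90 and size = 6.9%; with 24/15 weights, 0.91 and 6.8%. The 14-hour/fitting variance ratio of 1.54 (24/15 weights) has a 95% interval of about 0.81 to 2.9 (p about 0.18, ignoring pairing).

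**6. Osmolarity.** Table 8 SDs are 75.538 and 10.899 after insertion, and 34.473 and 58.943 at 14 hours. With equal strata V_fit = 2912 and V_14 = 2331, so k = 1.06 and size = 4.1%. By stratum the SDs move in opposite directions.

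**7. Illustration on the Table 11 case.** For -2.1 and SD 3 the standardised difference is 2.1/(3 × sqrt(2/27)) = 2.57. With k of 1.41 to 1.44, Φ(2.57 - 1.645 × k) is 58 to 60%; simulation gave 57%.

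**The case against.** **The structures might be meant to span both events.** A UN or CSH matrix over all replicates at both events would allow different variances. The text limits them to replicates within an event, and the separate time-within-subject effect for SP(POW) supports that reading. If spanning was intended, the wording has to say so.

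**Other provisions might rescue the model.** Kenward-Roger adjusts degrees of freedom and small-sample precision; it does not repair a wrong variance model. The transformation rule is a fairer objection. NIBUT is positive, with an SD of 61 to 68% of the mean after insertion, so the rule may well be used, and a log scale removes most of the excess. But it is triggered by non-normality, not by unequal variance over time, and some excess remains. Section 14.1 also defers detail to a stand-alone SAP, which could add a time-specific variance.

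**The NIBUT effect is conservative.** It cannot by itself create a false positive, and section 14.2 says that the sample size did not come from a power calculation. This limits the seriousness, but the loss is on a primary test and is avoidable.

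**Stronger readings that a reader might infer, and that the documents do not support:**

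- *That the TMH test is shown to be too liberal.* The historical ratio is compatible with equal variances, and at face value the excess is about two percentage points.
- *That osmolarity is materially distorted.* A factor of 1.17 arises only with the historical 25/16 weighting; at the planned equal strata it is about 1.06. The clearest feature of Table 8 is the opposite movement in the two strata, and between-strata heterogeneity is something the plan can accommodate.
- *That the trial's NIBUT power drops from 81% to about 57 to 60%.* This joins the Table 11 SD to the Table 6 variance ratio and implies a fitting SD of about 3 × sqrt(3) = 5.2 s or a little more, which no table gives.
- *That the SDs differ threefold.* Three is the NIBUT variance ratio; the SD ratio is about 1.8.

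**Conclusion.** The point holds as a specification defect in all three models, with a demonstrated consequence for NIBUT only. If the unadjusted Table 6 SDs recur with 27 per stratum, the 14-hour NIBUT interval is about 1.4 times too wide, the one-sided 5% test runs at about 1%, and power at -1.12 s is about 8% where 22% was available. Baseline adjustment of the assumed strength, or a log scale, would cut the factor to about 1.1 to 1.2. The direction is well supported, while the size depends on the historical SDs and on correlations that the documents do not give.

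For lower-lid TMH the historical SDs suggest a standard error of about 0.9 of the correct value and a size of about 7%, on a variance difference that is not established. For osmolarity the net factor of about 1.06 is minor.

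**What to change.** In section 14.5, and so in Part 2 through 14.7, choose one of these for NIBUT, TMH and osmolarity:

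1. Test each 14-hour hypothesis on the 14-hour data alone, with the subject mean of the replicates in a baseline-adjusted linear model. Lid margin staining is already analysed on 14-hour data only. Keep the two-event model for description.
2. Keep both time events, but give each its own variance parameters, for example with GROUP = time event or an unstructured 2 × 2 subject covariance across events.

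State the choice before database lock, and do not make it depend on a normality check. The cost is protocol and SAP wording, with no new data. Option 1 drops the fitting data from the test model; option 2 adds a few variance parameters.
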